13.8 Evaluation of Response

All participants included in the study will be assessed for response to intervention, even if there are major protocol deviations.

All of the participants who met the eligibility criteria, receive the study agent will be included in the intention-to-treat analysis. Since we will collect rectal biopsies at baseline, week 9 and 12, we will include the participants in the analysis if he/she provides biopsies at week 0 and week 9, but not week 12. Participants will be excluded if he/she only provides one biopsy. All conclusions regarding efficacy will be based on these participants.

Subanalyses may be performed on the subsets of participants, excluding those for whom major protocol deviations have been identified (e.g., early death due to other reasons, early discontinuation of intervention, major protocol violations, etc.). However, subanalyses may not serve as the basis for drawing conclusions concerning efficacy, and the reasons for excluding participants from the analysis

should be clearly reported. For all measurements of response, the 95% confidence intervals should also be provided.

We will conduct analysis by the grade of adenomas.

Biomarkers from Week-9 biopsies will also be used in the subanalysis in the intermittent arm.

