1. OBJECTIVES

1.1 Primary Objectives

The primary objective of the study is to test for the equivalency of the two aspirin schedules. We are going to evaluate the effects of a 3-month intervention of continuous versus intermittent aspirin dosing (i.e. 325 mg daily and 325 mg 3 weeks on/3 weeks off) on the ratio of cell proliferation (Ki-67) /apoptosis (BAX) in rectal biopsies.

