5.7 Adherence/Compliance

5.7.1 Participants will be considered evaluable if they have taken 80% of the prescribed doses.

5.7.2 Participant compliance will be monitored in a variety of ways. Patients will be required to keep a diary documenting drug dosing. Returned pills will be counted.

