7. CLINICAL EVALUATIONS AND PROCEDURES

7.1 Schedule of Events

	Clinic Visit 1: Screening	Clinic Visit 2: Baseline, within 6 weeks of Clinic Visit 1	Between-Visit Telephone or Email Contacts	Clinic Visit 3: 9 weeks after start of study agent [6]	Clinic Visit 4: 12 weeks after start of study agent [7]; or Off-Agent Visit [8]
Informed Consent	X				
Eligibility	X				
Registration/Randomization [1]	X				
Collect/Review Questionnaires [2]		X			
Medical History	X				
Physical [13]	X				
Vital Signs [12], Body Measurements [3]	X	X		X	X
Con Med Review	X	X		X	X
Assess Adverse Events	X	X		X	X
Pregnancy Test	X				
Blood Sample for Clinical Labs [10]	X	X		X	X
Blood Sample for Research [11]	X	X		X	X
Urine Sample [9]	X	X		X	X
Stool Sample	X	X		X	X
Rectal Swab		X		X	X
Rectal Biopsies [4]		X		X	X
Dispense Study Agent		X		X	
Collect/Count Unused Pills and Review Participant Diary				X	X
Telephone or Email Contact [5]			X		X [14]
Compensation	X				X

[1] Registration and randomization will occur between Clinic Visit 1 and Clinic Visit 2

[2] Clinic Visit 2: Food Frequency Questionnaire and Baseline Clinic Visit Questionnaire

[3] Height; weight; hip and waist circumferences

[4] Verify empty rectal vault prior to rectal biopsy procedure

[5] Phone or email contacts will include the following topics: compliance, adverse events, reminder to switch bottles, reminder to bring unused pills back to clinic. Participants will be contacted within 3 days after each biopsy visit (after Clinic Visits 2, 3, and 4), and at Weeks 1, 3, and 6 (± 3 days).

[6] Range: 8 weeks – 9 weeks and 2 days (56 – 65 days) after starting the study agent

[7] Range: 11 weeks – 12 weeks and 2 days (77 – 86 days) after starting the study agent

[8] If a participant comes off-agent (e.g. due to AE or concomitant medication), the Off-Agent Visit will be scheduled for as soon as possible after the participant stops the study agent.

[9] Urine samples will be obtained only from participants who agree to future unspecified research in the consent form.

[10] Clinic Visit 1-4: 1 green top tube for CMP and 1 purple top tube for CBC with differential. CMP and CBC will be processed on the day of the visit.

[11] 1 EDTA purple top tube for plasma, white blood cell (WBC), red blood cell (RBC); 1 red top tube for serum.

[12] ECOG performance status obtained at Screening Visit only. Vital signs include pulse, respirator rate, temperature, and blood pressure.

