8.3 Off-Agent Criteria

Participants may stop taking study agent for the following reasons:

- (1) Individuals who report minor upper GI symptoms such as dyspepsia, heartburn, dyspepsia, or heartburn who do not wish to remain on trial;
- (2) Inadequate agent supply;
- (3) Noncompliance (e.g. forget taking study agent);
- (4) Medical contraindication;
- (5) Concomitant medications.

Participants who go off-agent early will have an Off-Agent Visit (clinic visit 4 as listed in “7.1 schedule of events”) scheduled as soon as possible.

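### Section 13.8 rests the equivalence conclusion on the all-included set alone; a predefined adherent-set TOST should be required beside it, and the 80% rule in 5.7.1 reconciled with 13.8

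*Combined protocol and SAP*

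**What the plan says.** Section 1.1: "The primary objective of the study is to test for the equivalency of the two aspirin schedules". Section 13.4 tests this by TOST on the change from baseline to week 12 in the Ki-67/BAX ratio. Alpha is 0.05 and the margin is 3/4 SD (3.03 on the raw scale, 0.8423 on the log scale).

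Section 13.8 sets the population: "All participants included in the study will be assessed for response to intervention, even if there are major protocol deviations". Eligible participants who received study agent form what the plan calls its intention-to-treat analysis. Those with only one biopsy are dropped, and then "All conclusions regarding efficacy will be based on these participants". Of the alternative it says "Subanalyses may be performed on the subsets of participants", leaving out, for example, early discontinuation and major violations. It adds that "subanalyses may not serve as the basis for drawing conclusions concerning efficacy" and that reasons for exclusion should be reported.

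Early stoppers can reach the two-biopsy minimum. Section 8.3: "Participants who go off-agent early will have an Off-Agent Visit", with noncompliance among the listed reasons. Section 7.1, footnote 8: "the Off-Agent Visit will be scheduled for as soon as possible after the participant stops the study agent". Sections 7.1 and 7.4 include rectal biopsies at that visit.

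Section 5.7.1 states a different rule: "Participants will be considered evaluable if they have taken 80% of the prescribed doses". Nothing in section 13 refers to it.

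**The concern.** In a superiority trial, including non-adherent participants usually works against the claim. In an equivalence trial it can work for it: if participants in both arms stop taking capsules, the arms grow more alike whatever the schedules do. The scientific rationale in section 2.3 is biological, namely that the intermittent schedule has the same effect on proliferation and apoptosis as daily dosing. An equivalence result could therefore reflect similar biology or diluted exposure. The plan requires no analysis that would help tell these apart. If the optional analysis is run, its population has not been fixed in advance.

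The adherence rule adds a direct conflict. Under 5.7.1 a participant below 80% of doses is not evaluable; under 13.8 the same participant is analysed.

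**Working it through.** **Plan's own figure.** Inputs from 13.4: 32 per arm (40 less 20%), SD 4.04, margin ±3.03, alpha 0.05, true difference 0. Exact two-sample t TOST power is 0.814 against the stated 0.81. The power calculation is not in dispute.

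**Scale.** On the raw scale the baseline mean ratio is 2.54 and the ratio cannot fall below zero. If neither arm worsens, the mean changes can differ by at most 2.54, or 2.54/4.04 = 0.63 SD. That is inside the 0.75 SD margin, so the case does not arise there. It can arise on the log scale, which 13.4 uses if normality fails.

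**Illustration, in SD units on the log scale.**
- Margin 0.75, alpha 0.05 (13.4).
- Assumed full-adherence effects: daily 1 SD, intermittent 0.25 SD, so the true on-treatment difference is 1 − 0.25 = 0.75, exactly at the margin. The 1 SD is borrowed from a raw-scale expectation in 13.4.
- 32 adherent participants per arm plus k retained non-adherers who keep a fraction r of the effect. The plan allows for 8 of 40 per arm but does not split them between lost and retained, so k = 0, 4 and 8 are shown.
- Expected difference in the 13.8 set: 0.75 × (32 + rk)/(32 + k).
- Mixing adherers and non-adherers also widens the spread. For k = 8 and r = 0, the daily-arm variance is 1 + 0.2 × 0.8 × 1² = 1.16 and the intermittent-arm variance is 1 + 0.2 × 0.8 × 0.25² = 1.01.

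False equivalence relative to full adherence, by simulation (600,000 runs, mixture variance included):

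| Retained per arm (k) | Analysed per arm | Difference, r = 0 | False equivalence, r = 0 | Difference, r = 0.5 | False equivalence, r = 0.5 |
|---|---|---|---|---|---|
| 0 | 32 | 0.750 | 5.0% | 0.750 | 5.0% |
| 4 | 36 | 0.667 | 9.1% | 0.708 | 6.9% |
| 8 | 40 | 0.600 | 14.7% | 0.675 | 9.1% |

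The adherent set (32 per arm) stays at 5.0% throughout. Ignoring the extra spread, the k = 8, r = 0 cell would be 16.4%.

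**Direction.** With 20% no-effect non-adherence in one arm only (40 analysed per arm):
- Intermittent arm only: difference 1 − 0.8 × 0.25 = 0.80, false equivalence about 3%, which is conservative.
- Daily arm only: difference 0.8 × 1 − 0.25 = 0.55, about 21%.

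**What the 80% rule permits.** Twelve weeks is nominally 84 capsules. Missing 16 leaves 68/84 = 81%; missing 17 leaves 67/84 = 79.8%. So 16 is the most that passes. In the daily arm that is 16/84 = 19% of the aspirin. In the intermittent arm only 42 capsules are active, so up to 16/42 = 38% of the aspirin could be missed. Applied to active-period capsules, the rule allows 8 of 42 (19%), matching the daily arm.

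**How far disagreement between the two sets informs.** With 4 or 8 non-adherers retained per arm, the share of primary-set passes not matched by the adherent set is 39–68% when the on-treatment difference is at the margin. It is 7–12% when the arms are truly equal (1 SD effect each).

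**The case against.** The strongest reply is that 13.8 does choose its question. It calls the analysis intention-to-treat, includes deviators on purpose, and TOST holds 5% for that comparison. This stands. A reader might infer that the planned test has an inflated type I error; the documents do not support that. The percentages above are errors against a full-adherence target that the plan does not adopt.

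Three further objections also stand:
- A reader might infer that the analysis without deviators is forbidden or may not inform interpretation. The text bars it only as the basis for efficacy conclusions; it can be reported.
- A reader might infer that sections 3 and 13.4 give a third, conflicting rule because they count non-compliance within the 20% drop-out. Those are planning figures for attrition, not analysis rules. The real conflict is 5.7.1 against 13.8.
- 14.7% is not an expected value. It needs all 8 per arm to be retained with no effect and a true difference exactly at the margin, whereas 13.4 expects similar effects in both arms. Section 5.6 withdraws some participants from the study, and off-agent biopsies come soon after stopping, so partial effect is plausible. At 75% retained effect the figures are 5.9% (4 retained) and 6.9% (8 retained).

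The direction is also unknown. Section 2.3 hypothesises fewer side effects on the intermittent schedule, which would point to more stopping in the daily arm, but that is a hypothesis under test. Finally, an adherent set is selected after randomisation and cannot replace the primary set.

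None of this removes the gap: the analysis that would show whether equivalence survives among adherent participants is neither defined nor required.

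**Conclusion.** The point holds as a cheap improvement, not as a flaw in the primary test. Section 13.8 lets an equivalence conclusion stand without any required look at participants who took their assigned schedule, and leaves the 80% rule of 5.7.1 unused and in conflict with it.

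Under the stated assumptions, false equivalence relative to full adherence runs from about 5% to 15% with similar non-adherence in both arms, and falls to about 3% when non-adherence is confined to the intermittent arm. The size depends on four things the documents do not give: the lost/retained split, how much effect non-adherers keep, which arm they fall in, and a true difference near the margin. It also requires the log-scale analysis, unless an arm worsens on the raw scale.

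**What to change.** - Keep the 13.8 set as the primary analysis.
- Predefine one supportive adherent set: no major deviation, plus the 80% threshold of 5.7.1 applied to active-period capsules. Alternatively, apply it to all capsules and add an active-capsule sensitivity analysis.
- Make TOST in that set mandatory, with the same margin, 90% CI and missing-data rule as the primary (stating how the 13.6 imputation applies), and report it beside the primary result.
- Amend 13.8 so that the equivalence conclusion must address any disagreement between the two sets.
- State in both 5.7.1 and 13.8 that the 80% rule defines the supportive set and not the primary set.

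**Cost.** SAP wording and one repeat analysis; pill counts and diaries are already required by 5.7.2. No extra participants are needed. At the plan's 20% figure the adherent set has 32 per arm and power 0.81; with 5% or 10% excluded from 40 (38 or 36 per arm) it is 0.89 or 0.87. If losses went further, power would be 0.76 at 29 per arm and 0.69 at 26.

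**Downside.** When the arms are truly equal, about 7–12% of primary passes would go unmatched by chance, so disagreement calls for discussion and not automatic reversal. Requiring both sets to pass is not requested: it would lower power to about 0.86, 0.83 or 0.76 at 5, 10 or 20% non-adherence.

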13.9 Interim Analysis

There will be no interim analysis.

13.10 Ancillary Studies

NA

14. ETHICAL AND REGULATORY CONSIDERATIONS

14.1 Form FDA 1572

Prior to initiating this study, the Protocol Lead Investigator at the Lead or Participating Organization(s) will provide a signed Form FDA 1572 stating that the study will be conducted in compliance with regulations for clinical investigations and listing the investigators, at each site that will participate in the protocol. All personnel directly involved in the performance of procedures required by the protocol and the collection of data should be listed on Form FDA 1572.

14.2 Other Required Documents

14.2.1 Current (within two years) CV or biosketch for all study personnel listed on the Form FDA 1572 and Delegation of Tasks form for the Lead Organization and all Participating Organizations. CVs or biosketches do not need to be updated for participating study staff after drug shipment authorization (DSA).

14.2.2 Current medical licenses (where applicable) for all study personnel listed on Form FDA 1572 and Delegation of Tasks form for the Lead Organization and all Participating Organizations.

14.2.3 Lab certification (*e.g.*, CLIA, CAP) and lab normal ranges for all labs listed on Form FDA 1572 for the Lead Organization and all Participating Organizations.

14.2.4 Documentation of Good Clinical Practice training for all study personnel listed on the FDA Form 1572 and Delegation of Tasks form for the Lead Organization and all Participating Organizations.

14.2.5 Documentation of Federalwide Assurance (FWA) number for the Lead Organization and all Participating Organizations.

14.2.6 Signed Investigator's Brochure/Package Insert acknowledgement form

14.2.7 Delegation of Tasks form for the Lead Organization and all Participating Organizations signed by the Principal Investigator for each site and initialed by all study personnel listed on the form

14.2.8 Signed and dated NCI, DCP Financial Disclosure Form for all study personnel listed on Form FDA 1572 for the Lead Organization and all Participating Organizations

14.3 Institutional Review Board Approval

Prior to initiating the study and receiving agent, the Investigators at the Lead Organization and the Participating Organization(s) must obtain written approval to conduct the study from the appropriate IRB. Should changes to the study become necessary, protocol amendments will be submitted to the DCP PIO according to DCP Amendment Guidelines. The DCP-approved amended protocol must be approved by the IRB prior to implementation

14.4 Informed Consent

All potential study participants will be given a copy of the IRB-approved Informed Consent to review. The investigator will explain all aspects of the study in lay language and answer all questions regarding the study. If the participant decides to participate in the study, he/she will be asked to sign and date the Informed Consent document. The study agent(s) will not be released to a participant who has not signed the Informed Consent document. Subjects who refuse to participate or who withdraw from the study will be treated without prejudice.

Participants must be provided the option to allow the use of blood samples, other body fluids, and tissues obtained during testing, operative procedures, or other standard medical practices for further research purposes. If applicable, statement of this option may be included within the informed consent document or may be provided as an addendum to the consent. A Model Consent Form for Use of Tissue for Research is available through a link in the DCP website.

Prior to study initiation, the informed consent document must be reviewed and approved by NCI, DCP, the Consortium Lead Organization, and the IRB at each Organization at which the protocol will be implemented. Any subsequent changes to the informed consent must be approved by NCI, DCP, the Consortium Lead Organization's IRB, and then submitted to each organization's IRB for approval prior to initiation.

14.6 Other

This trial will be conducted in compliance with the protocol, Good Clinical Practice (GCP), and the applicable regulatory requirements.

Appendix A – Clinic Visit Instructions

Evaluating Intermittent Dosing of Aspirin for Colorectal Cancer Chemoprevention Study

CLINIC APPOINTMENT INSTRUCTIONS

1. You are scheduled for your clinic appointment on
_____ at _____ AM/PM.
2. Instructions for parking and how to get to the clinic are included in this packet.
3. If you need to change your appointment, please call XXXXXXXX at XXXXXXXX to reschedule.
4. Please read the detail “Stool Sample Instructions” and collect your stool sample before your clinic visit. We prefer that you collect the sample up to 3 days before the visit.
5. Remember to place your freezer ice pack into your freezer at least two days before your clinic appointment.
6. Please remember to bring to your visit your stool sample along with the ice pack in the foam cooler.
7. If you have any questions, please contact us at XXXXXXXXXX.

Thank you for your participation!

Appendix B – At-Home Stool Collection Instructions

Before you collect your stool sample:

1. We would like you to collect a stool sample up to 3 days before your clinic appointment.
2. You may request help reading these instructions from a member of your household, but please **do not let anyone handle** the containers, screw tops, or plastic bags.
3. At least 2 days before your clinic appointment, place the freezer pack into your freezer.

When you are ready to collect your stool sample:

1. Wash your hands with soap and warm water.
2. Urinate into the toilet and flush.
3. Lift the toilet seat.
4. Place the support frame on the toilet bowl rim. Place the white plastic bowl into the circle-shaped section of the frame.
5. Lower the toilet seat and pass the stool directly into the white plastic bowl. **Do not mix the stool sample with any urine or water from the toilet.**
6. Put on the gloves and open one of the stool collection containers (brown cap) with the spoon attached to the brown inner lid.
7. Using the spoon attached to the screw top, transfer pieces of stool into the container until the container is filled halfway. If the stool is liquid – pour. If the stool is loose – gently pour.
8. Screw the lid on the container tightly and wipe off any spills from the outside of the container with a clean paper towel. Discard the paper towel.
9. Repeat steps 6, 7, and 8 for the other brown cap stool collection containers.
10. Open the thin collection container with the light green lid.
11. Dip the sample wand attached to the lid into the stool sample which was collected in the white bowl. Cover the grooved portion of the sample wand completely with stool sample.
12. Re-insert the sample wand into the container and push the cap down until a *snap* is heard.
13. Place all 3 samples collection tubes (2 brown caps, 1 light green cap) into the plastic specimen bag and **seal the bag in zip-lock fashion**.
14. Write the **date and time of collection** on the bag with a pen or marker.
15. Place the sealed bag (containing the collection containers) into the second plastic bag. Remove any excess air from the bag and seal the second bag.
16. Wash your hands with soap and warm water. You may discard the gloves and the white stool collection bowl. The frame may be reused if future collections are expected.
17. **Place the sealed bag in the REFRIGERATOR until you bring it to your clinic appointment**

The day of your clinic appointment:

1. Put the sealed bag with the stool samples into the insulated transport bag along with the freezer gel pack.
2. Bring the package with you to your clinic appointment.

A.

B.

C.

This lid with spoon is for illustration only

D.

E.

F.

G.

Contents of Kit:

- a. (1) Collection bowl with lid and support frame for toilet rim**
- b. (2) Tubes with brown caps with spoons attached to inner lids**
- c. (1) Tube with light green cap with dipstick wand attached to inner lid**
- d. (1) Pair of non-allergenic nitrile gloves**
- e. (2) Plastic specimen bags**
- f. (1) Reusable transport bag**

Appendix C – Baseline Clinic Visit Questionnaire

Date: |_____|/|_____|/|_____| (mm/dd/yyyy)

We would like to learn more about your health conditions. Check the appropriate response choice for each question listed below. Please do not skip any of the questions and be careful to mark the correct column for each response choice.

PART 1: Health History

1. **Were any of your first-degree blood relatives, for example your mother, father, siblings, or children ever diagnosed as having cancer? (not including non-melanoma skin cancer)**

Yes
 No (Continue with Question 2)
 Don't Know (Continue with Question 2)

For each cancer diagnosis, please specify the relative, cancer site, and approximate age at diagnosis of cancer

RELATIONSHIP TO YOU (for example: sister)		CANCER TYPE (for example: breast)	AGE AT DIAGNOSIS		
1.					 years
2.					 years
3.					 years
4.					 years
5.					 years
6.					 years

2. **Were any of your first-degree blood relatives, for example your mother, father, siblings, or children ever diagnosed as having colon or rectal polyps?**

Yes
 No (continue with Question 3)
 Don't Know (continue with Question 3)

For each polyp diagnosis, please specify the relative and approximate age at diagnosis of polyps.

Reviewer: |_____|/|_____|/|_____|/|_____|/|_____| page 1 of 8

RELATIONSHIP TO YOU (for example: sister)		AGE AT DIAGNOSIS	
1.		 	years
2.		 	years
3.		 	years
4.		 	years
5.		 	years
6.		 	years

3. Has a doctor ever told you that you had any of the following conditions? Would you say yes, no, don't know? Please check the correct box. (Do not include borderline high cholesterol, fat; Do not include diabetes you only had when pregnant.)

Question	Answer		
Has a doctor ever told you that you had...	Yes	No	Don't Know
...high cholesterol?			
...high levels of fat (other than cholesterol)?			
... diabetes?			
...hypertension?			
...cardiovascular disease?			

PART 2: Medicines

1. Please list all medicines you have taken in the past 7 days. Please include the amount you took. (you may use the back of this page if needed):

	Name of each medicine	Dose/unit time
Example		
	Metformin	500 mg once daily
	Verapamil ER 240 mg	1 capsule daily
1.		
2.		
3.		
4.		
5.		
6.		
7.		
8.		
9.		
10.		
11.		
12.		
13.		
14.		
15.		
16.		
17.		
18.		
19.		
20.		
21.		
22.		
23.		
24.		
25.		
26.		
27.		
28.		
29.		
30.		
31.		
32.		

Reviewer: |_____|_____|_____|_____|_____|_____|_____| page 3 of 8

2. Have you ever regularly taken metformin? By regular, it means at least 3 days per week for at least twelve months in a row.

Yes
 No [Skip to Part 3]
 Don't Know [Skip to Part 3]

3. When you were regularly taking metformin, how many pills per day or how many per week did you take this medicine?

pills per day
 pills per week

4. When you were regularly taking metformin, how many months or years did you take this medicine?

Months
 Years

5. Are you still taking metformin regularly?

Yes
 No
 Don't Know

6. How many months or years ago did you stop using metformin regularly?

Months
 Years

PART 3: Supplements

1. Please list all supplements you have taken in the past 12 months. Please include the amount you took. Please do not list fish oil supplement here. (you may use the back of this page if needed):

	Name of each supplement	Dose/unit time
Example		
	Centrum calcium	1 tablet daily
	Multivitamin	1 capsule daily
1.		
2.		
3.		
4.		
5.		
6.		
7.		
8.		
9.		
10.		
11.		
12.		
13.		
14.		
15.		
16.		
17.		
18.		
19.		
20.		
21.		
22.		
23.		
24.		
25.		
26.		
27.		
28.		
29.		
30.		
31.		
32.		

Reviewer: |_____|_____|_____|_____|_____|_____|_____| page 5 of 8

2. Please list fish oil supplements you have taken in the past 12 months. Please include the amount you took. (you may use the back of this page if needed):

	Name of each supplement	Dose/unit time
Example		
	Omega-3 Fatty Acids	1 capsule daily
	Omega-6 Fatty Acids	1 capsule daily
1.		
2.		
3.		
4.		
5.		
6.		
7.		
8.		
9.		
10.		
11.		
12.		
13.		
14.		
15.		
16.		
17.		
18.		
19.		
20.		
21.		
22.		
23.		
24.		
25.		
26.		
27.		
28.		
29.		
30.		
31.		
32.		

Reviewer: |_____|_____|_____|_____|_____|_____|_____| page 6 of 8

(For women only)

Part 4: Gynecological and Reproductive History

1. Have you ever had a menstrual cycle or period?

Yes →

No

↓
CONTINUE
WITH
QUESTION 6.

2. How old were you when you menstruated for the first time (had your first period)? Years

3. Are you still having menstrual periods?

Yes →
 No

4. How old were you when your periods stopped completely?

Years

5. What was the reason your periods stopped? (Select only one answer)

- Natural menopause (change of life)
- Because of hysterectomy (either uterus and/or ovaries were surgically removed).
- Took medication that stopped periods
- Other (please specify): _____

6. Have you ever taken female hormone pills, skin patches, shots or crèmes other than birth control pills (for example estrogen, progesterone, estrogen and progesterone, conjugated estrogens, Premarin, Provera, Estraderm skin patches, or other not including Tamoxifen, Raloxifen, or Evista)?

↓
 Yes →
 No

↓
CONTINUE
WITH
QUESTION
11.

7. How old were you when you began taking them?

Years

8. How old were you when you last took them?

Years

9. Before you started taking female hormones, had your period stopped?

- Yes
- No

10. For many women, taking estrogens involves starting and stopping several times. During the time from starting to finally stopping your use of estrogens, how long, altogether were you actually taking them?

months

OR

years

(Fill in one only)

11. Have one or both of your ovaries ever been surgically removed?

- Yes-one ovary
- Yes-both ovaries
- No
- Don't Know

12. Have you ever given birth to a child?

- No (Continue with Question 16)
- Yes

13. How old were you when you gave birth to your first child?

--	--

 Years

14. How many pregnancies have you had that ended with a live birth?

--	--

 Number of live births

15. Of these pregnancies, how many were multiples births?

--	--

 Number of Multiple Births

16a. [Excluding the above pregnancies], did you have any other pregnancies; that is, pregnancies that ended in stillbirths, miscarriages, ectopic pregnancies, or induced abortions?

- Yes
- No

17. Have you ever taken oral contraceptives (birth control pills)?

- Yes →
- No
- Don't Know

18. How old were you when you begin taking them?

--	--

 Years

--	--

 Years

19. How old were you when you last took them?

- Still taking them

--	--

 Years

20. For many women, taking oral contraceptives involves starting and stopping several times. During the time from starting to finally stopping your use of oral contraceptives, how long, altogether were you actually taking the pills?

--	--

- months
- years

